8.5.1.4. Treatment of Outliers in Pharmacokinetic Analysis

If a value is considered to be anomalous due to being inconsistent with the expected PK profile, it may be appropriate to exclude the value from the PK analysis. However, the exclusion of any data must have strong justification and will be documented in the CSR.

Any quantifiable predose concentration value will be considered anomalous and set to missing for the PK analysis.

8.5.2. Presentation of Pharmacokinetic Data

Individual concentrations deemed to be anomalous will be flagged in the listings and excluded from the summary statistics.

For PK concentration data the following rules will apply:

- Values that are BLQ will be set to 0 for the calculation of summary statistics.
- Arithmetic mean or median values that are BLQ will be presented as 0.
- If any BLQ results (treated as 0) are in a series of summarized data, geometric mean and CV of geometric mean will be reported as not calculated (NC).

For PK parameters the following rule will apply:

- For the calculation of summary statistics of PK parameters, all not reported (NR) and not calculated (NC) values in a data series will be set to missing.
- The AUC values will be set to NC if they have been calculated using fewer than 3 concentrations, and/or 3 concentrations if the last is C_{max} .

- Geometric mean and CV will not be calculated for t_{max} .

8.5.3. Pharmacokinetic Statistical Methodology

All PK concentrations and parameters will be listed.

Summary tables, mean (+ standard deviation [SD]) figures, overlaying individual figures, and individual figures by hepatic function group and time postdose will be provided for plasma PK concentrations using CP and NCI-ODWG classifications separately. All PK concentration figures will be produced on both linear and semi-logarithmic scales. The +SD bars will only be displayed on the linear scale.

Summary tables by hepatic function groups will be provided for all PK parameters, with the exception of diagnostic regression-related PK parameters using CP and NCI-ODWG classifications separately. Summary statistics (n, Mean, SD, CV, minimum, median, maximum, geometric mean [Geom Mean] and geometric CV [Geom CV]) will be calculated for plasma LOXO-305 PK parameters and unbound PK parameters. Excluded subjects will be listed in the PK parameter tables, but will be excluded from the statistical analysis and summary statistics and noted as such in the tables.

In addition, summary statistics for protein binding will be tabulated separately by CP and NCI-ODWG hepatic function group.

8.5.3.1. Statistical Analysis

The primary analysis planned for this study is to evaluate the PK of LOXO-305 after a single dose in subjects with mild, moderate, or severe hepatic impairment, compared to subjects with normal hepatic function. To evaluate the effect of hepatic function group on the PK of a single dose of LOXO-305, paired t-tests will be performed for each hepatic impairment group (by CP classification) versus the normal group with respect to 1-to-1 matching on the natural log (ln)-transformed AUC_{0-t} , AUC_{0-inf} , and C_{max} . Geometric mean ratios and their corresponding 90% confidence intervals (CIs) will be calculated using the exponentiation of the mean difference and the CIs obtained for the difference in mean between each hepatic impairment group and the matching normal group.

CCI

In addition, an analysis of covariance (ANCOVA) will be performed on the ln- transformed AUC_{0-t}, AUC_{0-inf}, and C_{max}. The ANCOVA model will contain a categorical factor of population for subjects with varied-degree hepatic impairment (severe, moderate, and mild by CP classification) and healthy matched-control subjects, a categorical covariate (sex), and continuous covariates (age and BMI). Ratios of least squares means and 90% CIs will be calculated using the exponentiation of the difference between hepatic function cohort least squares means from the ANCOVA analyses on the ln-transformed AUC_{0-t}, AUC_{0-inf}, and C_{max} with the normal group as reference. In addition, an ANCOVA will be performed on the lntransformed unbound AUC_{0-t}, unbound AUC_{0-inf}, and unbound C_{max}. Similar ANCOVA analysis will be applied for evaluating the effect of hepatic function group by NCI-ODWG classification.

CCI

Additionally, a scatterplot of the ln-transformed PK parameters (AUC_{0-t}, AUC_{0-inf}, and C_{max}) and corresponding unbound PK parameters versus screening/baseline Child-Pugh total score and its individual components will be produced. The linear regression will be included on the plot, along with two-sided 90% confidence bands for the linear regression line. The Spearman rank correlation coefficient will also be calculated

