4.7. Matching Process

A matched-control healthy subject will be matched to hepatically impaired subjects (age $[\pm 10 \text{ years}]$, BMI $[\pm 20\%]$, and sex). An individual matched-control healthy subject may be matched with up to 1 subject within each hepatic impairment group (ie, to a maximum of 3 hepatically impaired subjects across the study [1 mild, 1 moderate, and 1 severe], but to no more than 1 subject in each impairment group). A listing of the matched subjects will be included in the Clinical Study Report.

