8.4.2. Statistical Methodology

The primary analysis planned for this study is to evaluate the PK of LOXO-305 after a single dose in subjects with mild, moderate, or severe hepatic impairment, compared to subjects with normal hepatic function. To evaluate the effect of hepatic function group on the PK of a single dose of LOXO-305, paired t-tests will be performed for each hepatic impairment group (by CP classification) versus the normal group with respect to 1-to-1 matching.

In addition, an analysis of covariance (ANCOVA) will be performed on the natural log (In)-transformed AUC_{0-t}, AUC_{0-inf}, and C_{max}. The ANCOVA model will contain a categorical factor of population for subjects with varied-degree hepatic impairment (severe, moderate, and mild by CP classification) and healthy matched-control subjects, a categorical covariate (sex), and continuous covariates (age and BMI). Ratios of least squares means and 90% confidence intervals (CIs) will be calculated using the exponentiation of the difference between hepatic function cohort least squares means from the ANCOVA analyses on the In-transformed AUC_{0-t}, AUC_{0-inf}, and C_{max}. In addition, an ANCOVA will be performed on the natural log (In)-transformed unbound AUC_{0-t}, unbound AUC_{0-inf}, and unbound C_{max}. The specific procedures will be documented in the SAP. Similar ANCOVA analysis will be applied for evaluating the effect of hepatic function group by NCI-ODWG classification.

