3. STUDY ENDPOINTS

3.1. Primary Endpoints

The following PK parameters will be calculated whenever possible, based on the plasma concentrations of LOXO-305:

- maximum observed plasma concentration (C_{max})

-
- time to maximum observed plasma concentration (t_{max})
 - area under the concentration-time curve (AUC) from hour 0 to the last measurable concentration (AUC_{0-t})
 - area under the concentration-time curve from hour 0 extrapolated to infinity (AUC_{0-inf})
 - percentage extrapolation for AUC_{0-inf} (% AUC_{extrap})
 - apparent terminal elimination rate constant (λ_z)
 - apparent plasma terminal elimination half-life ($t_{1/2}$)
 - apparent systemic clearance (CL/F)
 - apparent volume of distribution at the terminal phase (V_z/F)
 - mean residence time extrapolated to infinity (MRT_{inf}).

In addition, a single blood sample will be collected predose to determine the fraction unbound (f_u) of LOXO-305 in plasma and, whenever possible, the following PK parameters will be calculated for unbound LOXO-305 using f_u : unbound C_{max} ($C_{max,u}$), unbound AUC_{0-t} ($AUC_{0-t,u}$), unbound AUC_{0-inf} ($AUC_{0-inf,u}$), unbound CL/F (CL/F, u), and unbound V_z/F ($V_z/F,u$).

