5. SAMPLE SIZE JUSTIFICATION

A total of up to 24 subjects with hepatic impairment (up to 8 subjects from each hepatic impairment group, per CP classification) and approximately 8 to 24 matched-control healthy subjects with normal hepatic function will be enrolled in the study with the goal of having at least 6 subjects from each hepatic impairment group per CP classification and at least 6 subjects with normal hepatic function complete the study. Of these hepatic impairment subjects enrolled per CP category, enrollment will also aim to have at least 4 subjects meet severe hepatic impairment criteria per National Cancer Institute-Organ Dysfunction Working Group (NCI-ODWG) classification, at least 4 subjects meet moderate hepatic impairment criteria per NCI-ODWG classification, and at least 4 subjects meet mild hepatic impairment

criteria per NCI-ODWG classification. The sample size chosen for this study was based upon precedent set by other PK studies of similar nature and was not based on power calculations to detect statistically significant differences among groups. This number is considered a sufficient sample size to evaluate the PK of LOXO-305 under various degrees of hepatic function.

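### Do the unbound primary endpoints need a paired comparison beside the ANCOVA?

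*SAP*

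**What the plan says.** SAP 3.1 lists the total parameters as primary endpoints and adds that, where possible, "the following PK parameters will be calculated for unbound LOXO-305", using each subject's unbound fraction.

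SAP 8.5.3.1 then sets out the comparisons by Child-Pugh group.

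- **Total AUC0-t, AUC0-inf and Cmax, paired.** The t-tests are run "with respect to 1-to-1 matching on the natural log (ln)-transformed" values of these three parameters. "Geometric mean ratios and their corresponding 90% confidence intervals (CIs) will be calculated" from the paired differences.
- **Total AUC0-t, AUC0-inf and Cmax, ANCOVA.** The model has population (normal, mild, moderate, severe), sex, age and BMI. It yields least-squares mean ratios and 90% intervals with normal as reference.
- **Unbound AUC0-t, AUC0-inf and Cmax.** "In addition, an ANCOVA will be performed on the lntransformed unbound" parameters. The readable text names no paired test for them.

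Protocol 8.4.2 states the paired analysis without naming parameters: "paired t-tests will be performed for each hepatic impairment group (by CP classification) versus the normal group with respect to 1-to-1 matching". It also gives the unbound parameters an ANCOVA. In the SAP, a redacted block follows the paired-test paragraph and another follows the ANCOVA paragraph.

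**The concern.** The unbound parameters are primary endpoints, and Protocol 1.5 says that liver disease can alter protein binding and that the study is to inform dosing recommendations. Yet total exposure gets two group comparisons and unbound exposure one.

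The one that remains has a known weakness. An ordinary ANCOVA estimates a single residual variance from all four groups. If severe subjects are more variable than the rest, that estimate is too small for the severe-versus-normal contrast and the 90% interval is too narrow, most of all when a large control group dominates the pooled variance. The paired interval avoids this. A control may be matched to up to three impaired subjects, "but to no more than 1 subject in each impairment group", so the pairs within one comparison are independent and their differences carry their own variance.

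At stake would be an interval for unbound exposure in severe impairment that claims more precision than it has, with no second interval beside it.

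**Working it through.** **Inputs from the documents.** Up to 8 subjects per impaired group, with a goal of at least 6 completing (SAP 5). For controls, "approximately 8 to 24 matched-control healthy subjects with normal hepatic function will be enrolled"; the low end means controls shared across groups, the high end separate controls. The interval level is 90% (SAP 8.5.3.1). The variability figures in Protocol 1.4.2 are redacted, and no other readable passage gives group variances. Every SD below is therefore an assumption.

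**Step 1: the plan's own figure.** With equal log-scale SDs (0.40) in all groups, simulated coverage of the pooled ANCOVA interval is 89.8% to 90.2% for 6 or 8 per impaired group and 6, 8, 18 or 24 controls. The nominal 90% is reproduced.

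**Step 2: the mechanism.** Ignore covariates and set the normal-group SD to 1. Take 8 per impaired group and 24 controls, with only the severe group at SD 1.5.

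- Pooled variance = (23 + 7 + 7 + 7 × 2.25)/44 = 52.75/44 = 1.199.
- SE used by the model = √[1.199 × (1/24 + 1/8)] = 0.447.
- True SE = √(1/24 + 2.25/8) = 0.568.
- Coverage ≈ P(|Z| < 1.68 × 0.447/0.568) = P(|Z| < 1.32) ≈ 0.81.

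**Step 3: the same formula under other patterns.**

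- *Severe group less variable (SD 0.7), same group sizes.* Pooled variance = (37 + 7 × 0.49)/44 = 0.919. Model SE = √(0.919/6) = 0.391. True SE = √(1/24 + 0.49/8) = 0.321. Coverage ≈ P(|Z| < 2.05) ≈ 0.96. The interval is now too wide.
- *Four groups of equal size n, moderate and severe both at SD k.* Pooled variance = (1 + 1 + k² + k²)/4 = (1 + k²)/2. Model SE² = (1 + k²)/2 × 2/n = (1 + k²)/n. True SE² = 1/n + k²/n. The two agree for every k, so severe-versus-normal coverage is nominal.

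**Step 4: simulation with covariates** (5,000 trials per scenario; base log-SD 0.4). Coverage of the nominal 90% pooled interval, severe versus normal:

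| Assumed SD ratio to normal | 6–8 shared controls | 18–24 controls |
|---|---|---|
| All equal | 0.90 | 0.90 |
| Severe alone 1.25 | 0.87–0.88 | 0.85–0.86 |
| Severe alone 1.5 | 0.86 | 0.81 |
| Severe alone 2 | 0.82–0.83 | 0.74 |
| Moderate and severe 1.5 | 0.90 | 0.84 |
| Moderate and severe 2 | 0.90 | 0.80 |
| All impaired 1.5 | 0.92 | 0.87 |
| All impaired 2 | 0.94 | 0.85 |
| Severe alone 0.7 | 0.93 | 0.95–0.96 |

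The paired interval covers 0.89 to 0.91 throughout. So the effect can be under-coverage, none or over-coverage, and the documents do not say which row applies.

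**Step 5: the price of the paired interval.** With equal variances, its log-scale half-width against the pooled one is 0.444 against 0.401 (6 per group, 6 controls; ratio 1.11), 0.367 against 0.341 (8 and 8; 1.08), 0.445 against 0.325 (6 and 18; 1.37) and 0.367 against 0.278 (8 and 24; 1.32). SAP 8.5.1.2 excludes AUC0-inf values with more than 30% extrapolation, and one lost value removes a whole pair. At log-SD 0.4, going from 6 pairs to 5 widens the expected half-width from 0.44 to 0.51. Nor does the paired test adjust for age and BMI differences left within the matching limits; the ANCOVA does.

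**Step 6: what the plan already provides.**

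- SAP 8.5.3 says that summary statistics, including SD and geometric CV, "will be calculated for plasma LOXO-305 PK parameters and unbound PK parameters", by hepatic function group. Unequal spread would show.
- SAP 8.5.3 lists every subject's parameters, and Protocol 4.7 puts the matched subjects in a listing in the study report. Unbound exposure is total exposure times the unbound fraction (SAP 8.5.1), so each paired log difference is the total-exposure difference plus the difference in log unbound fraction. A reader can form the paired unbound comparison from these.
- SAP 1 allows supplementary analyses, identified as such in the report.

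**Step 7: does primary-endpoint status call for a paired test?** SAP 3.1 also lists tmax, CL/F and mean residence time as primary endpoints, and the readable text gives them no paired test. The SAP does not apply every comparison to every listed parameter. The unbound ANCOVA was also a deliberate addition: Protocol Appendix 5 records that it entered Section 8.4.2 on a regulator's recommendation.

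**The case for a change.** The strongest case for the concern is that the asymmetry is real and cheap to remove. Protocol 8.4.2 does not limit the paired tests to total exposure; the SAP does. Unbound values exist for each subject, so a paired analysis needs no new data. Tabulated SDs would reveal unequal spread, but choosing a different interval after seeing them would be post hoc. Greater variability in severe disease is a pattern one might expect, and with 18 to 24 controls it is the pattern in which the pooled interval does worst.

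Most of this stands as an argument for an optional extra. The restriction to total exposure is on the page, the mechanism is standard, and an interval named in advance is better than one chosen later.

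It does not make the plan wrong. The expected pattern has no figure in the documents behind it. That the ANCOVA pools its variance is inferred from the usual meaning of the term; the readable SAP states no variance structure, and the redactions sit where such detail would go. What is blacked out cannot be counted as absent. Adding a paired interval while keeping the ANCOVA would leave two unbound intervals, with no rule for which to believe if they disagree.

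**Conclusion.** The concern does not hold. The readable SAP does give the unbound parameters an ANCOVA and no paired test, but that is a defensible choice which follows the protocol.

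The possible miscalibration is conditional. For severe versus normal, coverage of the nominal 90% interval lies between 0.74 and 0.96 over the assumed SD ratios of 0.7 to 2, and is 0.90 with equal variances or, with shared controls, when moderate and severe are equally more variable. These figures rest on an ordinary pooled fit, a base log-SD of 0.4, linear covariate effects and no extra correlation within pairs. None of these is given in the readable documents.

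The consequence is also limited. No decision rule depends on these intervals, SAP 8.1 already asks for caution because the sample size has no power basis, and the planned tables and listings would show unequal spread and allow the paired comparison to be formed. Whether to name an extra sensitivity analysis in advance is a matter on which reasonable statisticians differ. No change is required.

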8.6. Safety and Tolerability Assessments

8.6.1. Adverse Events

All AEs will be coded using the Medical Dictionary for Regulatory Activities (MedDRA) Version 23.0. All AEs will be assigned severity grade using Common Terminology Criteria for Adverse Events (CTCAE) Version 5.0.

A treatment-emergent adverse event (TEAE) will be defined as an AE that starts during or after LOXO-305 dosing, or starts prior to LOXO-305 dosing and increases in severity after LOXO-305 dosing.

A treatment-related TEAE will be defined as a TEAE with a relationship of related to the study treatment (LOXO-305), as determined by the investigator.

All AEs will be listed. In addition to the data recorded in the database, the listings will include derived onset time and duration. Onset time will be calculated from the time of dosing for TEAEs only.

The frequency of subjects with TEAEs and the number of TEAEs will be summarized for the following categories:

- TEAEs (overall, serious, leading to discontinuation, and leading to death) by hepatic function group
- TEAEs by severity and hepatic function group
- Treatment-related TEAEs (overall, serious, leading to discontinuation, and leading to death) by hepatic function group
- Treatment-related TEAEs by severity and hepatic function group

The frequency of subjects will be summarized separately for TEAEs and treatment-related TEAEs by the following:

- System organ class, preferred term, and hepatic function group
- Preferred term and hepatic function group For the AE data the following rules will apply:
 - For the derivation of TEAE status: If the start date/time of an AE is incomplete or missing, an AE will be assumed to be a TEAE, unless the incomplete start date/time or the end date/time indicates an AE started prior to dosing.
 - For the derivation of treatment-related TEAE status: If the study treatment relationship for a TEAE is missing, a TEAE will be assumed to be a treatment-related TEAE.

- For the derivation of onset time: If the start date/time of an AE is missing, onset time will not be calculated. If the start date/time of an AE is incomplete, where possible, the minimum possible onset time will be calculated and presented in ‘ \geq DD:HH:MM’ format (eg, if the date/time of dosing is 01MAY2019/08:00 and recorded start date/time of an AE is 03MAY2019, then the minimum possible onset time will be calculated by assuming the AE started at the first hour and minute of 03MAY2019 [03MAY2019/00:00], thus will be presented as onset time \geq 01:16:00 in the listing).
- For the derivation of duration: If the end date/time of an AE is missing, duration will not be calculated. If the start or end date/time of an AE is incomplete, where possible, the maximum possible duration will be calculated and presented in ‘ \leq DD:HH:MM’ format (eg, if the start of an AE date/time is 01MAY2019/08:00 and its recorded end date/time is 03MAY2019, then the maximum possible duration will be calculated by assuming the AE ended at the last hour and minute of 03MAY2019 [03MAY2019/23:59], thus will be presented as duration \leq 02:15:59 in the listing).
- For the calculation of summary statistics: If a subject experienced multiple TEAEs with the same preferred term for the same treatment, this will be counted as 1 TEAE for that treatment under the maximum severity recorded.

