6. STUDY TREATMENT AND HEPATIC FUNCTION GROUPS

The planned treatment administered for all subjects will be 200 mg LOXO-305.

The hepatic function group names and ordering to be used in the TFLs are presented in [Table 1](#) and [Table 2](#).

Table 1: Presentation of Hepatic Function Groups in TFLs by CP classification (Safety and PK)

Hepatic Function Group	Child-Pugh Classification	Abbreviation	Order in TFLs
Normal Hepatic Function	NA*	Normal	1
Mild Hepatic Impairment	5 or 6 points (Class A)	Mild	2
Moderate Hepatic Impairment	7 to 9 points (Class B)	Moderate	3
Severe Hepatic Impairment	10 to 15 points (Class C)	Severe	4

*Only subjects with hepatic impairment will have CP scores calculated at screening and Day -1. Hepatically impaired subjects will be assigned to groups according to CP scores at Check in (Day -1)

All hepatic function groups described above are the planned groups. The TFLs will reflect the actual hepatic function groups dosed based upon their CP score unless otherwise stated.

Table 2: Presentation of Hepatic Function Groups in TFLs by NCI-ODWG classification (PK)

Hepatic Function Group	NCI-ODWG Classification	Abbreviation	Order in TFLs
Normal Hepatic Function	Total Bilirubin: \leq ULN AST: \leq ULN *	Normal	1
Mild Hepatic Impairment	Total Bilirubin: > ULN to 1.5 x ULN AST: >ULN	Mild	2
Moderate Hepatic Impairment	Total Bilirubin: >1.5 to 3 x ULN AST: Any	Moderate	3
Severe Hepatic Impairment	Total Bilirubin: > 3 – 10 x ULN AST: Any	Severe	4

Abbreviations: AST = aspartate aminotransferase; NCI-ODWG = National Cancer Institute-Organ Dysfunction Working Group; ULN = upper limit of normal.

*Only subjects with hepatic impairment will have NCI-ODWG scores calculated at screening and Day -1. Hepatically impaired subjects will be assigned to groups according to NCI-ODWG scores at Check in (Day -1)

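### If a preferred term recurs within a subject, the SAP's one-per-term rule understates the number of TEAEs that the same section promises, overall and by grade

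*SAP*

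**What the plan says.** SAP Section 8.6.1 announces two quantities for its first set of adverse event tables: "The frequency of subjects with TEAEs and the number of TEAEs will be summarized for the following categories". The categories are the overall table (with serious events, discontinuations and deaths), "TEAEs by severity and hepatic function group", and the treatment-related versions, including "Treatment-related TEAEs by severity and hepatic function group". The second set, by system organ class and preferred term, gives subjects only: "The frequency of subjects will be summarized separately for TEAEs and treatment-related TEAEs by the following".

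The data rules that close the section include one on repeats. It opens "For the calculation of summary statistics: If a subject experienced multiple TEAEs with the same preferred term for the same treatment" and ends "this will be counted as 1 TEAE for that treatment under the maximum severity recorded". It is not tied to either set of tables and makes no exception for event counts.

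SAP Section 6 states: "The planned treatment administered for all subjects will be 200 mg LOXO-305". Section 8.6.1 also states "All AEs will be listed", and Section 8.6.6 plans no inference on safety data.

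**The concern.** Counting a subject once per term, at the worst grade, is a sound convention for numbers of subjects. This rule, however, defines what counts as one TEAE, and the number of TEAEs is itself a promised output. The section therefore promises an event count and gives a rule that does not count events.

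Safety and tolerability is the secondary objective. Each impairment group enrols up to 8 subjects, with a goal of at least 6 completing; the control group may enrol 8 to 24. In an impairment group of that size, a few repeats of one term can visibly change the event count. The rule also does not say which seriousness, relationship or discontinuation status a collapsed event keeps, although the tables are split by those attributes.

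**Working it through.** The plan gives no event figure to reproduce, so the check is to apply the rule literally.

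**Inputs from the documents**
- Outputs: subjects and events, overall and by severity (SAP 8.6.1).
- Rule: repeats of a term in a subject count as 1 TEAE at the maximum grade (SAP 8.6.1).
- Treatments: one (SAP 6). The restriction to the same treatment therefore excludes nothing, and every postdose repeat in a subject collapses.

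**Overall count**
- True number of TEAEs = number of TEAE records, R.
- Number under the rule = number of distinct subject-by-term pairs, P.
- With m = R/P mean records per pair, shortfall = (R - P)/R = 1 - 1/m.
- P can never exceed R, and is lower as soon as one term recurs in one subject.

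The documents give no value for m, so the range is assumed:

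| m | Shortfall |
|---|---|
| 1.0 | 0% |
| 1.1 | 9.1% |
| 1.25 | 20% |
| 1.5 | 33.3% |
| 2 | 50% |
| 3 | 66.7% |

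If m were equal in all groups, ratios of event counts between groups would be preserved. If m differed, they would not be.

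**By grade (invented subjects)**
- Headache at Grades 1, 1 and 2 plus nausea at Grade 1. True count: 4 events, 3 at Grade 1 and 1 at Grade 2. Under the rule: 2 events, 1 at each grade. The Grade 2 count stays at 1, two Grade 1 events disappear, and the Grade 1 share falls from 3/4 = 75% to 1/2 = 50%.
- Headache at Grades 2 and 2. True count: 2 events. Under the rule: 1 event at Grade 2.

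Within a subject-by-term pair the grade distribution therefore shifts upward, or stays put if all repeats share one grade. A pooled table shifts upward when the dropped records are Grade 1 episodes beneath a higher grade. Same-grade repeats can pull it the other way: adding a Grade 1 nausea to the second subject changes the Grade 2 share from 2/3 = 67% to 1/2 = 50%.

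**A check against the protocol's own experience**

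The term list for study LOXO-BTK-20006 (Protocol Section 1.6) has 8 entries if the diarrhea marked as occurring twice is counted twice. If both episodes were in one subject, the rule gives 7, a shortfall of 1/8 = 12.5%. If they were in different subjects it gives 8, with no shortfall. The protocol states a total of 7 AEs in 3 subjects but does not say how the repeated term was counted or who reported it, so this illustrates the effect without estimating m.

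**The case against.** The strongest reply is that the rule was meant for subject counts only, where the convention fits, and that the table shells accompanying the SAP may show this. They are not available here, so the intent cannot be settled. It could also be read as the SAP's deliberate definition of a counted TEAE. Neither reading is stated. The section itself separates tables of subjects and events from tables of subjects only, so its authors treated events as a distinct quantity.

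Other points on that side stand. Protocol Section 8.5 commits only to incidence by severity and relationship, not to an event count. The study gives a single dose with confinement to Day 8, and after discharge only drug-related AEs and SAEs are reported, so recurrence may be rare. In two of the three healthy-volunteer experiences described in Protocol Section 1.6, no term is shown as repeated. These were small studies without impaired subjects, so they do not bound m here.

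A reader might infer more than the text supports:
- That milder episodes are moved into a higher grade and inflate it. They are dropped; no grade's count rises.
- That event counts will certainly be too low. They are exact if no term recurs within a subject.
- That 67% is an expected size. It comes from an assumed m of 3.
- That the tables could not be reconciled with the listings. Every event is listed and the rule is printed, so a reader could reproduce the collapsed count.

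**Conclusion.** The point holds on the SAP text, with limited reach. Section 8.6.1 promises a number of TEAEs and prescribes a rule that returns the number of distinct subject-by-term pairs. Followed literally, the rule understates event counts, overall and within any grade from which records are dropped, whenever a term recurs in a subject. The size depends entirely on m, which the documents do not give: 0% at m = 1, and 9% to 67% over an assumed range of 1.1 to 3.

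The effect stops at descriptive event counts. Numbers of subjects, the system organ class and preferred term tables, and the listings are unaffected, and no test or interval depends on these counts. The protocol's narrower commitment does not resolve the conflict, because SAP Section 1 gives the SAP precedence on statistical matters and Protocol Section 8.6 has the tables programmed from it. This is a minor wording correction, worth making because two programmers could reasonably produce different numbers from the present text.

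**What to change.** Replace the repeats rule in SAP Section 8.6.1 with wording such as: In numbers of subjects, a subject with several TEAEs of the same preferred term is counted once for that term, at maximum severity; in numbers of TEAEs, every TEAE record is counted at its own grade, with its own seriousness, relationship and outcome.

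If the collapsed count is what is wanted, relabel those columns as numbers of subject-by-preferred-term occurrences, or drop the event counts, and state which attributes a collapsed event keeps. Check the table shells against whichever wording is chosen.

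The preferred fix costs one SAP sentence. It needs no new data, no extra tables and no protocol change.
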